#### 2.2 Secondary objectives

- **2.2.1** To assess study accrual rates and compliance with the therapy.
- **2.2.2** To characterize the safety and adverse event profile of two doses of oxybutynin in the study population.
- **2.2.3** To evaluate the consistency of the results across the various methods used to evaluate the efficacy of oxybutynin (i.e., hot flash scores versus hot flash frequencies, mean differences versus 50% or greater reduction since baseline, single day versus full week to define patients' baseline hot flash scores).
- **2.2.4** To compare patient-reported quality of life and hot flash interference, as measured by the HFRDIS, across arms.
- **2.2.5** To compare other changes in patient symptoms, as measured by the Symptom Experience Questionnaire, across arms.

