#### 8.2 Dose Modifications

Dose modifications to the patient's cancer treatment are up to the discretion of the treating physician. During participation in the study, if the patient develops any symptoms attributed to the drug that are considered to be of unacceptable severity by the patient and/or physician, oxybutynin/placebo doses will be adjusted as follows:

Dose modifications for adverse events				
Low Dose	Maintain prescribed dose, but decrease frequency from BID to once daily.			
(2.5 mL BID)	If symptoms are still unacceptable by the patient and/or physician, drug will be discontinued and patient will be taken off study.			
High Dose (5.0 mL BID)	If toxicity occurs, decrease dose from 5 mL BID to 2.5 mL BID. If symptoms persist, decrease dose from 2.5 mL BID to 2.5 mL once daily. If symptoms are still unacceptable by the patient and/or physician, the drug will be discontinued and patient will be asked to complete questionnaires to date and then be taken off study.			

**Urinary retention**: For patients on both doses, if at any time during treatment, the patient develops severe urinary symptoms, he should immediately discontinue study treatment and get a post void residual ultrasound assessment as clinically indicated.

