#### 11.4 Symptom Experience Questionnaire (Appendix V)

The Symptom Experience Questionnaire is collected at the end each of the 7 weeks of the study period. This form collects patient reported toxicity and quality of life data using a 0-10 scale, with one question that allows an unstructured response to report symptoms not captured in the questions provided. Estimated completion time for the Symptom Experience Questionnaire is 10-15 minutes each week.

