
Weekly hot flash frequencies (as opposed to weekly hot flash scores) will be compared across the oxybutynin and placebo arms in a manner similar to above using a mixed model that accounts for the observed distribution of weekly hot flash frequencies. A fixed sequence procedure will be employed. For the responder analysis, patients who experience a 50% or greater reduction in hot flash frequency since baseline will be deemed responders, while the remaining patients (including those with missing hot flash frequencies) will be deemed non-responders. Finally, consistency of the results will be assessed across the various methods used to evaluate the efficacy of oxybutynin in this trial (i.e., hot flash scores versus hot flash frequencies, mean differences versus 50% or greater reduction since baseline, single day versus full week to define patients' baseline hot flash scores).

**To assess safety**, the proportion of patients experiencing a grade 3 or higher adverse event will be summarized by arm. We expect this proportion to be extremely low for all arms.

To assess tolerability, mixed models similar to the one described above will be estimated that include baseline and weekly patient-reported symptoms as measured by the Symptom

Experience Questionnaire (Appendix V) across the 6-week treatment period. A single mixed model will be developed for each patient-reported symptom. Estimates from the mixed models will be used to construct 90% confidence intervals for mean differences in patient-reported symptoms between the oxybutynin and placebo arms (i.e., Arm A versus Arms C and D combined; Arm B versus Arms C and D combined) at 6 weeks post-randomization. Contrasts estimated via the mixed models will involve a two-sided *t*-test with a nominal significance level of  $\alpha = .10$ .

**To assess feasibility**, the time required to accrue 87 patients will be reported. To move forward with a phase III trial, an average accrual rate of 4 patients per month (starting 4 months after enrollment begins, to account for the time required for multiple institutions to activate the trial) would be desired. The treatment adherence rate (i.e., the number of patients who completed treatment per protocol divided by the number of patients who started treatment) will be summarized by arm.

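### Patient-reported side effects are compared between arms only at week 6, after symptom-driven dose reductions and stops, which may understate the burden over the six treatment weeks

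*Combined protocol and SAP*

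**What the plan says.** Secondary objective 2.2.5 is "To compare other changes in patient symptoms, as measured by the Symptom Experience Questionnaire, across arms". Section 11.4 sets the schedule: "The Symptom Experience Questionnaire is collected at the end each of the 7 weeks of the study period", which is one baseline and six on-treatment assessments.

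The tolerability paragraph of section 13.4 specifies models that "include baseline and weekly patient-reported symptoms as measured by the Symptom" Experience Questionnaire, one per symptom. The estimates are used to "construct 90% confidence intervals for mean differences in patient-reported symptoms between the oxybutynin and placebo arms", and the time point is given as "Arm B versus Arms C and D combined) at 6 weeks post-randomization". I read this as the end of the sixth treatment week (Day 49). Counted literally from randomization it would fall about a week earlier, because treatment starts on Day 8. No weekly, averaged or worst-score comparison is named.

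Section 8.2 acts on the same symptoms. When they are "considered to be of unacceptable severity by the patient and/or physician, oxybutynin/placebo doses will be adjusted as follows", the high-dose row begins "If toxicity occurs, decrease dose from 5 mL BID to 2.5 mL BID", then goes to 2.5 mL once daily, then stops the drug. The low-dose row has one reduction and then a stop.

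**The concern.** A symptom severe enough to trigger section 8.2 leads to a lower dose, and the lower dose may reduce the symptom. Section 1.2 describes the usual side effects as resolving once the drug is discontinued, so some fading after a reduction is what the protocol itself would lead one to expect. A man with marked dry mouth in weeks 1-2 who is then reduced can report a low score at week 6. That score is observed, so the missing-data sensitivity analysis in section 13.4 does not reach it.

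The other planned summaries do not fill the gap. Section 13.4 expects grade 3 or higher events to be very rare in every arm. The adherence rate counts men who completed treatment per protocol, and a man reduced under section 8.2 may count as one of them. What is at stake is the picture of tolerability, including the cognitive items of section 1.3.4, that would inform a phase III trial.

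**Working it through.** **1. The plan's own figure.** No figure is given for tolerability. Section 13.5 states 76% power for the primary comparison, from 26 men per oxybutynin arm, 13 + 13 = 26 on placebo, two-sided alpha .10, intraclass correlation .50, standardized difference 0.50 and six weekly scores.

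- SD of a six-week average = sqrt((1 + 5 × 0.5)/6) = 0.764
- Standard error = 0.764 × sqrt(2/26) = 0.212
- 0.50/0.212 − 1.645 = 0.715, so power = 76.3%. The stated figure reproduces, as a comparison of six-week averages.
- Week 6 alone: SD = 1, standard error 0.277, and 0.50/0.277 − 1.645 = 0.158, so power is about 56%. With baseline adjustment, SD = sqrt(1 − 0.5²) = 0.866 and power is about 67%.

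For a symptom with a constant moderate effect, the weekly average is therefore the more precise contrast even if no dose is changed.

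**2. Dose path in section 8.2.** High dose: 10 mL/day, then 5, then 2.5 (25% of the assigned amount), then stop. Low dose: 5 mL/day, then 2.5 (50%), then stop.

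**3. Attenuation at week 6.** Let r be the share of an oxybutynin arm reduced or stopped by week 6, and f the share of the side effect remaining in those men. Both are assumptions. Then week-6 difference / full-assigned-dose difference = 1 − r(1 − f).

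| r | f = 0 | f = 0.25 | f = 0.50 |
|---|---|---|---|
| 5% | 0.95 | 0.96 | 0.975 |
| 10% | 0.90 | 0.925 | 0.95 |
| 20% | 0.80 | 0.85 | 0.90 |
| 30% | 0.70 | 0.775 | 0.85 |
| 40% | 0.60 | 0.70 | 0.80 |

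At r = 0 the ratio is 1.

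**4. Simulation of the high-dose steps.** Assumed: symptom score with SD 2, intraclass correlation 0.5, mean drug effect 1.5 or 2.5 points, effect proportional to dose, and a step down whenever the score passes a threshold. With 7% to 34% of active patients modified, the week-6 contrast showed 71% to 94% of the full-dose difference, and the weeks 1-6 average showed 83% to 99%. With more than half modified, week 6 fell to 45% to 63%. Results were nearly the same whether men who stopped were followed or taken off study. Dose reduction drove most of the attenuation.

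**5. Effect on power.** Assumed: 26 men per group; 30% of the 5.0 mL arm have a 5-point rise in weeks 1-2 and the rest +0.5; between- and within-man SD 1.4; baseline mean 1.5.

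| Rise remaining in affected men | Week-6 contrast | Worst score minus baseline |
|---|---|---|
| 1 point | about 30% | 90% |
| 2.5 points | 61% | 90% |
| No modification | 87% | 93% |

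In the first row the weeks 1-6 average reached 82% to 85%.

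**6. A symptom that builds over time.** With an effect rising from 0.2 to 1.2 points by week 6, power was 66% at week 6, 53% for the worst score and 48% to 49% for the average. In expected values, let the effect be w/6 of its final size in week w, with 20% of men cut to half effect from week 4. Week 6 is then 1 − 0.2 × 0.5 = 0.90. The average is [(1+2+3)/6 + 0.9 × (4+5+6)/6]/6 = (1.0 + 2.25)/6 = 0.54.

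**The case against.** The strongest reply is that the week-6 contrast is a proper treatment-policy estimate for a secondary objective in a trial that calls itself a pilot. The documents also give no reason to expect many dose reductions. Section 1.2 reports mostly mild effects and no arm difference in discontinuation in the earlier trial in women. Attributed grade 2 events are reported (section 9.2), and weekly calls ask about dry mouth, dizziness and urinary retention (Appendix VII). Time is nominal with an arm-by-time term, so weekly differences can already be read from the model.

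Most of this stands and limits the point. Discontinuation is not dose reduction, however, and none of these items is a planned between-arm comparison of patient-reported burden during treatment.

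A reader might infer more than the documents support:

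- That burden is understated as a fact. No modification rate is given, and the severe loss of power in step 5 needs affected men to fall to a 1-point rise.
- That week 6 is always the least sensitive week. Step 6 shows the opposite for a symptom that builds.
- That comparing levels fails an objective about changes. Under randomization the expected arm difference is the same for both, and baseline is in the model.
- That the comparison of the two doses is biased. None is planned: each dose is compared only with placebo. Nor does the plan classify any man as tolerating his dose.

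**Conclusion.** The point holds as a limitation of what is compared. Symptoms are measured every week, but arms are compared at one week that follows the protocol's own symptom-triggered reductions and stops. The week-6 estimate may understate the six-week burden if side effects fall with dose and some men are modified. Over the assumed ranges the shortfall against the full-dose difference is about 2% to 40%, and it is zero if nobody is modified. The true size cannot be derived from the documents.

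Replacing week 6 with the worst score is not justified. The worst score depends on how many weeks are observed, and it does less well than week 6 for a symptom that builds. The right response is to add to the week-6 contrast.

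**What to change.** In the tolerability paragraph of section 13.4:

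- Keep the week-6 contrast as the end-of-treatment estimate.
- Add, for each symptom item, the arm difference averaged over treatment weeks 1-6 from the mixed model already planned (Arm A and Arm B each versus combined placebo, 90% CI).
- Give the worst post-baseline score relative to the Day 7 score as a supporting summary.
- Report by arm the number and timing of dose reductions and stops for symptoms. Confirm that the case report forms capture reductions: the Appendix IV diary counts doses, not volume, so it would not show a change from 5 mL to 2.5 mL twice daily.

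Separately, reconcile section 8.2 and the toxicity paragraph of section 12.3.2, which take a man off study after a toxicity stop, with the opening of section 12.3.2, which expects data submission to continue. This determines which weekly scores exist.

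The cost is SAP wording and a little extra analysis of questionnaires already collected. The added intervals join a family tested at .10 without adjustment and should be read as estimates. The worst score's dependence on weeks observed is a real drawback, which the weekly average cross-checks.

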#### 11.5 Hot Flash Related Daily Interference Scale (HRFDIS) (Appendix VI)

Hot Flash Related Daily Interference Scale (HFRDIS), a tool developed by [name].[33] We recently asked 10 men with androgen deprivation hot flashes, to review this tool. All of the HFRDIS items were assessed as clear, appropriate, and easy to interpret. The items related to work and sexuality were identified as potentially difficult to answer if the individual was retired or not sexually active, however all of the men were able to provide a numeric score for these items. We also discussed the above with [name], who developed the HFRDIS tool and have identified other studies that have used the HFRDIS in men receiving androgen deprivation therapy [34-36]. These studies provide additional data supporting the reliability and validity of the 10-item instrument in this population.

The Hot Flash Related Daily Interference Scale is to be completed by all participants at baseline (Week 1) and at the conclusion of the study (Week 7). It will also be completed at the end of Weeks 2 and 4 of study treatment, as it asks questions related to hot flashes over the past two weeks. This 10-item questionnaire uses a 1-10 scale to assess the interference caused by hot flash symptoms with specific aspects of patients' personal lives. Each completion of the HFRDIS is expected to take 5 minutes.

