To assess patient-reported quality of life and hot flash interference, mixed models similar to the one described above will be estimated that include patients' scores on the HFRDIS (Appendix VI) across the 6-week treatment period. A single mixed model will be developed for each HFRDIS item. Estimates from the mixed models will be used to construct 90% confidence intervals for mean differences in patient-reported quality of life and hot flash interference between the oxybutynin and placebo arms (i.e., Arm A versus Arms C and D combined; Arm B versus Arms C and D combined) at 6 weeks post-randomization. Contrasts estimated via the mixed models will involve a two-sided *t*-test with a nominal significance level of  $\alpha = .10$ .

Attempts to minimize **missing data** will be made through site training and data monitoring (e.g., form delinquency notifications, queries; see Section 6.1.3). The proportion of, and reported reasons for, missing data will be presented by time point and arm. Correlation analysis and logistic regression analysis will be used to examine whether baseline patient characteristics and prognostic factors predict missingness. The primary analysis will provide unbiased parameter estimates under a missing completely at random or missing at random mechanism. However, a sensitivity analysis will be conducted to assess the robustness of the results across various assumptions about the missing data.

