#### 13.5 Sample Size and Power

As this is a pilot trial, the sample size was determined based on feasibility and logistical considerations rather than on power for hypothesis testing. We aim to enroll 26 evaluable patients per oxybutynin arm and 13 evaluable patients per placebo arm (i.e., 78 evaluable patients total). For the primary aim, 26 evaluable patients per oxybutynin arm and 13 evaluable patients per placebo arm with 6 weekly hot flash scores provide 76% power to detect a mean difference in hot flash score reduction from baseline when comparing each oxybutynin arm (5.0 mL twice daily or 2.5 mL twice daily to the placebo arm (both placebo arms combined) based on a two-sided *t*-test estimated via a mixed model, nominal significance level of  $\alpha = .10$ , intraclass correlation of .50, and population standardized mean difference of 0.50 (i.e., Cohen's convention for a moderate effect size)[44]. In a similar study in women, Cohen's *d* equaled 0.85 when comparing the higher dose oxybutynin arm (2.5 mL twice daily escalated to 5.0 mL twice daily) to the placebo arm [45]. An additional 9 patients will be accrued to account for a 10% loss in sample size due to ineligibility, major treatment violation, or cancellation. Maximum projected accrual is, therefore, 87 patients.

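### The week-6 contrasts for the HFRDIS and the symptom items are not adjusted for the Day 7 baseline score

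*Combined protocol and SAP*

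**What the plan says.** Section 13.4 defines the primary contrast as the difference between arms in hot flash score reduction from baseline to 6 weeks. The model takes baseline and weekly scores as responses, with nominal time, arm and arm by time as fixed effects. Nothing constrains the arms to share a baseline mean.

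The two patient-reported analyses in the same section are worded differently:

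- **Symptoms.** The models are described as similar to the primary one and explicitly include baseline. The estimates are "mean differences in patient-reported symptoms between the oxybutynin and placebo arms" at 6 weeks.
- **HFRDIS.** The models are again described as similar, and they cover patients' "scores on the HFRDIS (Appendix VI) across the 6-week treatment period". Baseline is not named. The estimates are "mean differences in patient-reported quality of life and hot flash interference between the oxybutynin and placebo arms" at 6 weeks.

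Section 5.0 (Study Calendar) and Section 7.1 place both instruments at the end of the baseline week, before study drug. Objective 2.2.5 is "To compare other changes in patient symptoms, as measured by the Symptom Experience Questionnaire, across arms". Objective 2.2.4, for the HFRDIS, asks for a comparison across arms and does not mention change. Section 13.4 also permits stratification factors, baseline characteristics and prognostic factors as covariates if the arms turn out to be imbalanced.

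**The concern.** Read as written, these contrasts compare week-6 levels, and a man's own starting level does not enter the comparison. Many items will not start at zero. Section 1.0 links hot flashes to fatigue and poor sleep, and Section 11.2 describes urinary symptoms in men with prostate cancer. Randomization is stratified on hot flash frequency, hot flash duration and prior therapies (Section 4.5.1), so no symptom or HFRDIS item is balanced directly.

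With 26 men per comparison group, a chance difference at baseline passes into the week-6 difference in proportion to the baseline to week-6 correlation. In the one trial that is run, this can look like benefit or harm of a dose. The intervals are also wider than the collected data require.

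**Working it through.** **Inputs.** Section 13.5: 26 men per oxybutynin arm, 13 + 13 = 26 pooled placebo, two-sided alpha .10, effect 0.50 SD, intraclass correlation .50 (given for hot flash scores). No correlation is given for the HFRDIS or symptom items, so I take r = 0.3, 0.5 and 0.7 as assumptions. Scores are in SD units with equal variance at baseline and week 6. Week 6 means the end of the sixth treatment week.

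**The plan's own figure.** Section 13.5 says the sample sizes "provide 76% power to detect a mean difference in hot flash score reduction from baseline", "based on a two-sided *t*-test estimated via a mixed model". With v the variance of the analysed quantity,

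power ≈ Φ(0.50 / √(2v/26) − 1.645).

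For the mean of six weekly scores, v = (1 + 5 × 0.5)/6 = 0.583. Then 0.50/0.212 = 2.360 and power = 76.3%, which reproduces 76%. A single week-6 level has v = 1 and does not reproduce it (56.3%). The 76% therefore rests on averaging over weeks, and it cannot be carried over to a week-6 contrast on another instrument.

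**Does baseline in the model adjust the contrast?** With a free mean for every arm at every time point and complete data, the fitted means are the observed cell means. The week-6 contrast is then the raw week-6 difference. A simulation (78 men, correlation 0.5 between all time points, 800 replicates) agreed: the largest gap was 7 × 10⁻¹⁶. With dropout at random and the four HFRDIS time points, the SD of the week-6 estimate was:

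| Dropout | No baseline | Baseline, free means | Baseline, common mean |
|---|---|---|---|
| 15% | 0.294 | 0.290 | 0.257 |
| 30% | 0.323 | 0.320 | 0.293 |

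Baseline with free means helps very little. A common baseline mean does help.

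**Chance imbalance.** The standard error of a baseline difference is √(2/26) = 0.277 SD. Per comparison, the chance of a gap above 0.25 SD is 37%, and above 0.50 SD it is 7%. There are 22 scored symptom items with a baseline and 10 HFRDIS items, each with two dose contrasts: 32 × 2 = 64 comparisons. About 64 × 0.071 = 4.6 would be expected to start more than 0.50 SD apart. An expected fraction r of any gap carries into the week-6 difference, which is half of it at r = 0.5.

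**Precision.** The variance factors are 1 for the level, 2(1 − r) for simple change and 1 − r² for the baseline-adjusted contrast. Each standard error is 0.277 × √factor, and the 90% half-width is 1.645 times that.

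| r | SE level / change / adjusted | Half-width level / change / adjusted | Power level / change / adjusted |
|---|---|---|---|
| 0.3 | 0.277 / 0.328 / 0.265 | 0.456 / 0.540 / 0.435 | 56.3% / 45.2% / 59.7% |
| 0.5 | 0.277 / 0.277 / 0.240 | 0.456 / 0.456 / 0.395 | 56.3% / 56.3% / 66.9% |
| 0.7 | 0.277 / 0.215 / 0.198 | 0.456 / 0.353 / 0.326 | 56.3% / 75.3% / 81.0% |

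Adjustment reduces the standard error by 1 − √(1 − r²) = 4.6%, 13.4% and 28.6%. At r = 0.5 this is worth 1/0.75 − 1 = 33% more patients. With the noncentral t on 75 degrees of freedom, power is slightly lower: 55.7% for the level, 66.2% adjusted at r = 0.5 and 80.4% at r = 0.7.

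**The case against.** A reader might infer that the plan ignores the Day 7 scores. The documents do not support that. Section 13.4 puts baseline in the symptom model, and calling the HFRDIS model similar to the primary one points to baseline there too. Leaving out the word may only reflect that the HFRDIS is not weekly.

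A reader might also infer bias. There is none over randomization: the unadjusted difference is unbiased, and its interval already allows for variation from baseline imbalance. Nor do both objectives ask for change, since only 2.2.5 does.

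The strongest defence is that the plan uses week-6 wording loosely. Section 13.1 describes the primary endpoint as scores at 6 weeks, yet Section 13.4 tests reduction from baseline, so a change contrast may be intended here as well. This stands as a real ambiguity, but it does not dispose of the point. A change contrast is not baseline-adjusted either: it carries a baseline gap with reversed sign (expected fraction r − 1), gains nothing at r = 0.5 and loses precision below that.

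The covariate provision is only a partial answer. It is optional, triggered by the observed data, has no threshold and does not name the baseline item score. It is also fair that these are secondary endpoints in what Section 13.5 calls a pilot trial, with no power target set for them, and that the gain at r = 0.3 is small.

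**Conclusion.** The point holds as one of precision and chance imbalance. As written, both sets of contrasts are week-6 levels without baseline adjustment, and including baseline as a response with free arm means does not change that materially. For symptoms, the estimate also does not match the change asked for in objective 2.2.5.

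The loss is small to moderate if r is between 0.3 and 0.5, and substantial at 0.7. It rests on assumed correlations, equal variances, 26 evaluable men per group and near-complete data. The 0.50 SD effect is a yardstick borrowed from the primary endpoint, not a target that the plan sets here. The documents do not support reading this as a biased analysis or as one that discards the baseline. It is worth correcting because the data are already collected.

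**What to change.** In Section 13.4, name the Day 7 score in the HFRDIS model, as is already done for symptoms. For both instruments, state that the reported contrast is the baseline-adjusted difference between arms at week 6. Either form will do:

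- the baseline item as a covariate, with its interaction with time; or
- baseline as a response, with one mean common to all arms.

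With baseline adjusted, the arm difference in week-6 level equals the arm difference in change, so this also answers objective 2.2.5. A simple change score should not be used instead. Items with no baseline question, such as 23b in Appendix V, stay unadjusted.

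The cost is a few sentences in the analysis plan and one covariate (or one constraint) per model, with no new data. Men with a missing baseline item need the baseline-as-response form if they are to stay in the analysis.
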